## 5.3. Secondary Endpoints

Bleeding complications have an expected incidence of 36% for unilateral TKA (Bierbaum et al. 1999), and are not rare. These will be assessed separately as a secondary safety endpoint at discharge based on the incidence of transfusions required (autologous or allogenic) as a result of bleeding.

Descriptive safety analyses for the incidence of the individual adverse events comprising the composite will also be performed.

The secondary endpoints also include a comparison of post-operative alignment outcomes other than coronal mechanical axis to the pre-operative alignment goals, and assessment of improvements in Knee Society Scores and SF-12 Health Survey scores.

**Table 1: Summary of Primary TKA Complications Assessed in the Primary Safety Endpoint**

Complications of Primary TKA (29)	Knee Society Definition (29)	Literature-Based Incidence Rate for Primary TKA	Method for Assessing Complications
1. Medial Collateral Ligament Injury	Intraoperative or early postoperative medial collateral ligament injury requiring repair, reconstruction, a change in prosthetic constraint, revision surgery, or TKA protocol	2.7% (30)	Incidence of intraoperative or postoperative MCL transection or avulsion leading to repair, reconstruction, change in prosthetic constraint, or revision TKA.
2. Extensor Mechanism Disruption	Disruption of the extensor mechanism (surgical repair and/or extensor lag should be recorded)	2.1% (31)	Incidence of iatrogenic extensor mechanism disruption.
3. Neural Deficit	Postoperative neural deficit (sensory or motor) related to the index TKA	1.3% (32)	Incidence of sensory or motor neural deficit (complete or incomplete) related to the TKA procedure.
4. Periprosthetic Fracture	Periprosthetic fracture of the distal femur, proximal tibia or patella (operative or nonoperative treatment should be recorded)	0.68% (32)	Incidence of periprosthetic fracture of the distal femur, proximal tibia or patella. Operative and nonoperative treatment for the fracture will also be recorded.
5. Patellofemoral Dislocation	Dislocation of the patella from the femoral trochlea (direction of instability should be recorded)	0.5% (33)	Incidence of patella dislocation from the femoral trochlea due to postoperative instability. The direction of instability will also be recorded.

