Success/Failure Criteria	
The study success criterion is to simultaneously demonstrate that the malalignment rate is less than or equal to 0.16 (effectiveness endpoint) and that the composite safety event rate is less than 0.136 (safety endpoint) based on one-sided exact binomial tests with type 1 error rate equal to 0.05. A p-value <math>\leq 0.05</math> for both tests will indicate study success.

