## 5.2. Primary Safety Endpoint

The primary endpoint is a composite endpoint that includes a number of relevant adverse events associated with manual TKA that were defined and published by the Knee Society (Healy et al. 2011), each having an expected incidence  $\leq 2.7\%$  based on a literature search summarized in Table 1. The sum of these relatively rare complications is equal to 7.6%. The percentage of patients with TCAT-assisted implantation experiencing the composite safety event will be compared to 7.6% plus a non-inferiority margin of 7.0%.

*Note: The primary safety endpoint will be evaluated utilizing only the IDE Study Arm.*

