**THINK Surgical, Inc.**

Proprietary rights of THINK Surgical, Inc. are involved in the subject matter of this material. It is submitted in confidence for a specific purpose and the recipient by accepting this material agrees that it will not be used other than for the express purpose for which it was delivered. Disclosure to others without written permission from THINK Surgical, Inc. is forbidden.

Complications of Primary TKA (29)	Knee Society Definition (29)	Literature-Based Incidence Rate for Primary TKA	Method for Assessing Complications
6. Tibiofemoral Dislocation	Dislocation of the tibiofemoral joint (direction of instability should be recorded)	0.2% (34)	Incidence of iatrogenic tibiofemoral joint dislocation. The direction of instability will also be recorded.
7. Vascular Injury	Intraoperative vascular injury requiring surgical repair, bypass grafting, or stenting (compartment syndrome or amputation should be reported)	0.15% (32)	Incidence of iatrogenic vascular injury requiring surgical repair, bypass, grafting, or stenting. Incidents of compartment syndrome or amputation will also be recorded.

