#### THINK Surgical, Inc.

Proprietary rights of THINK Surgical, Inc. are involved in the subject matter of this material. It is submitted in confidence for a specific purpose and the recipient by accepting this material agrees that it will not be used other than for the express purpose for which it was delivered.

Disclosure to others without written permission from THINK Surgical, Inc. is forbidden.

assumed. Using industry standard software (nQuery Advisor 7.0, Module POT0x-1), it was determined that statistical power to reject the non-inferiority hypothesis was equal to 82.5% with a sample size of N=103. Because of the discreteness of the exact binomial distribution, the power curve is not monotonic. Power for sample sizes of N=102, 103, 104, 105, 106, 107, 108, 109, 110, 111, 112, 113, 114, 115, 116, 117, 118, 119, 120, 121 and 122 are 71.9%, 82.5%, 81.8%, 81.1%, 80.3%, 79.6%, 78.9%, 78.1%, 77.3%, 76.6%, 75.8%, 84.9%, 84.3%, 83.7%, 83.1%, 82.5%, 81.8%, 81.1%, 80.5%, 79.8%, and 87.6%. The smallest sample size with power  $\geq 80\%$  is 103. For sample sizes of N=103 and above, power never falls below 75.8%. The minimum sample size for which power remains at least equal to 80% at that value for all larger values is N=113.

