**The total sample size to be enrolled is equal to 115 (103 plus 10% for possible loss-to-follow-up).**

It can be noted that with N=103, the number (%) of patients experiencing the primary composite safety event must be no larger than 8 (7.8%) in order to achieve the primary study success criterion. With 8 of 103 patients experiencing the event, the upper bound of the one-sided 95% exact binomial confidence interval will be 0.1358 which is less than 0.136, thereby permitting rejection of the inferiority hypothesis and a conclusion of no clinically significant increase in the incidence of the composite safety endpoint.

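### Table 1 counts only iatrogenic extensor disruption and tibiofemoral dislocation, a limit that the paired Knee Society definitions do not carry and that the 7.6% reference is not shown to share

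*Combined protocol and SAP*

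**What the plan says.** Section 5.2 builds the composite from "relevant adverse events associated with manual TKA that were defined and published by the Knee Society" and adds up their literature rates to obtain the 7.6% reference. Table 1 sets out three things for each complication: the Knee Society definition, the literature rate and what the trial will count.

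- **Row 2, extensor mechanism (2.1%).** The definition covers any disruption and asks only that repair or lag be noted. The trial counts "Incidence of iatrogenic extensor mechanism disruption".
- **Row 6, tibiofemoral dislocation (0.2%).** The definition covers any dislocation of the joint. The trial counts "Incidence of iatrogenic tibiofemoral joint dislocation".
- **Row 5, patellofemoral dislocation (0.5%).** The trial counts "Incidence of patella dislocation from the femoral trochlea due to postoperative instability". The definition does not name a cause but does ask for the direction of instability.

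The rate column is described only as literature-based incidence for primary TKA. The plan does not define iatrogenic. Section 5 has the investigator evaluate complications, and Section 10.4 has the investigator assign relationship to the device. The independent core lab in Section 15 reads the radiographic efficacy endpoints only, and no independent review of safety events is described.

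**The concern.** A non-inferiority test against a fixed literature rate needs the trial's events and the reference events to be defined alike. In rows 3 and 7 the Knee Society definition itself carries a limit (related to the index operation; intraoperative), and the assessment column carries a corresponding one. In rows 2 and 6 the limit appears only in what the trial counts.

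Every patient receives the device, so the person judging whether an event was iatrogenic is unblinded. Follow-up runs 6 to 12 months, so a late disruption, for example after a fall, could be judged not iatrogenic and leave the primary count. A narrower count against an unchanged threshold cannot raise the number of events. If the benchmark is all-cause, the mismatch can therefore only help the device pass its primary safety test.

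**Working it through.** **Inputs**

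- Test: Section 1 (Success/Failure Criteria) judges success "based on one-sided exact binomial tests with type 1 error rate equal to 0.05".
- Threshold 0.076 + 0.06 = 0.136, N = 103, success at 8 events or fewer, assumed true device rate 0.0608: Section 9.1.
- Row rates: Table 1. They sum to 2.7 + 2.1 + 1.3 + 0.68 + 0.5 + 0.2 + 0.15 = 7.63, rounded in the plan to 7.6.
- Share *f* of row 2 and row 6 events that would be called iatrogenic: not in the documents. Range used: 0 to 1.

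Section 5.2 gives a margin of 7.0%, which conflicts with the 0.06 in Sections 1 and 9.1. That is a separate matter: at N = 103 both margins give a limit of 8 events.

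**The plan's own figures**

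The limit is the largest c with P(X ≤ c | 103, 0.136) ≤ 0.05. P(X ≤ 8) = 0.0494. With 9 events the one-sided 95% upper bound is 0.1475, above 0.136, so c = 8. Power is P(X ≤ 8 | 103, 0.0608) = 0.8252, which agrees with Section 9.1: "statistical power to reject the non-inferiority hypothesis was equal to 82.5% with a sample size of N=103".

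**Effect of the restriction**

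Rows 2 and 6 carry 2.1 + 0.2 = 2.3 points, or 2.3/7.63 = 30% of the reference. Assume that the cited rates are all-cause, that the true rate on the full definitions is exactly 0.136, and that the device's excess risk lies outside the excluded events. Then

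counted rate = 0.136 − (1 − f) × 0.023.

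A reference cut down to match the count, with the 0.06 margin kept, gives a threshold equal to that same number. The last column shows the limit that such a threshold would allow.

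| f | Counted rate | P(X ≤ 8), N = 103 | Limit if the reference were matched |
|---|---|---|---|
| 1 | 0.1360 | 4.9% | 8 |
| 0.75 | 0.1303 | 6.8% | 7 |
| 0.5 | 0.1245 | 9.3% | 7 |
| 0.25 | 0.1188 | 12.5% | 6 |
| 0 | 0.1130 | 16.4% | 6 |

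**By row, with the whole row excluded**

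- Extensor: 0.136 − 0.021 = 0.115, chance of passing 15.0%.
- Tibiofemoral: 0.136 − 0.002 = 0.134, chance of passing 5.5%.

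**Sensitivity**

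- If all 115 enrolled patients are analysed, the limit is 9. The chances at f = 1, 0.5 and 0 are then 4.0%, 8.1% and 15.1%.
- If the excess risk is instead spread over all components in proportion, the counted rate at f = 0 is 0.136 × 0.053/0.076 = 0.0948 and the chance of passing is 34.9%. The 16.4% therefore belongs to its stated assumption and is not a worst case.

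**The case against.** **The benchmark may not be all-cause.** The rate column gives no case definition. The sources for rows 2 and 6 (references 31 and 34) date from 2006 and 2001, before the Knee Society list (2011 in Section 5.2, 2013 in the reference list). The rates cannot have been collected under that list, and sharing a table row does not show a shared definition. If those sources counted only surgery-related events, there is no bias, and deleting the word would create a mismatch against the device. This stands, and it is why the conclusion is conditional. It also means that the plan does not show that count and benchmark agree.

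**Iatrogenic may mean no more than arising from the procedure.** That would fit row 3 and the section's reference to events associated with TKA, and few events would then drop out. Limiting a device composite to procedure-caused events is also a defensible choice. This stands in part: such a choice needs a definition, a named judge and a reference on the same basis, and the plan gives none of these.

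**Excluded events stay on file.** Section 10.1 defines adverse events without regard to relatedness, so an all-cause count can be produced. This lowers the cost of the fix but leaves the primary test as it is.

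**Row 5.** A reader might add its 0.5 points (2.8 in all) and infer a chance of passing of 20.6%. The documents do not support that. The definition in row 5 already refers to instability, so the qualifier may exclude little. Row 1 differs in both directions: limiting the injury to transection or avulsion is narrower, and dropping the restriction to early events is wider. Neither row supports a quantified bias.

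**Conclusion.** The mismatch between definition and count in rows 2 and 6 is in the text, and any bias that results runs toward success. A reader might go further and infer that the safety test is in fact tilted and its type 1 error inflated. The documents do not establish this. It needs two facts that they do not give: that the 2.1% and 0.2% are all-cause, and that the undefined word would really exclude events.

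If the rates are all-cause and the device's excess risk lies outside the excluded events, the chance of passing at a true full-definition rate of 13.6% lies between 4.9% (no effect) and 16.4% (every such event excluded), against a nominal 5%. The allowed count on a matched reference would lie between 8 and 6. In substance this is a concern about the extensor row; tibiofemoral dislocation alone hardly moves the result.

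**What to change.** In the assessment column of Table 1, delete *iatrogenic* from rows 2 and 6, so that the primary composite counts every event meeting the Knee Society definition, as Section 5.2 describes. Record cause as an attribute of each event and report the iatrogenic-only rate as a sensitivity analysis.

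If the sponsor can show that the sources for the 2.1% and 0.2% counted only iatrogenic events, keep the restriction, state that basis and define the term. This choice should rest on the sources, without sight of the causes of observed events.

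For consistency, also align rows 5 and 1 with their Knee Society definitions.

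The cost is table wording. The events are already collected as adverse events, so no visits, procedures or patients are added. The downside for the sponsor is that the observed rate may be slightly higher.

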**THINK Surgical, Inc.**

Proprietary rights of THINK Surgical, Inc. are involved in the subject matter of this material. It is submitted in confidence for a specific purpose and the recipient by accepting this material agrees that it will not be used other than for the express purpose for which it was delivered. Disclosure to others without written permission from THINK Surgical, Inc. is forbidden.

Complications of Primary TKA (29)	Knee Society Definition (29)	Literature-Based Incidence Rate for Primary TKA	Method for Assessing Complications
6. Tibiofemoral Dislocation	Dislocation of the tibiofemoral joint (direction of instability should be recorded)	0.2% (34)	Incidence of iatrogenic tibiofemoral joint dislocation. The direction of instability will also be recorded.
7. Vascular Injury	Intraoperative vascular injury requiring surgical repair, bypass grafting, or stenting (compartment syndrome or amputation should be reported)	0.15% (32)	Incidence of iatrogenic vascular injury requiring surgical repair, bypass, grafting, or stenting. Incidents of compartment syndrome or amputation will also be recorded.

## 6. SELECTION OF STUDY POPULATION

### 6.1. Inclusion Criteria

In order to be eligible for the study, candidates must meet the following criteria:

- a) Is at least 21 years of age.
- b) Is skeletally mature, as evidenced by closed epiphyses.
- c) Is eligible for primary unilateral TKA due to osteoarthritis defined radiographically by a Kellgren-Lawrence Grade of 3 or higher.
- d) Is able to understand and willing to comply with the requirements of the study.
- e) Is able to give voluntary, written informed consent to participate and has signed an Informed Consent Form specific to this study.

### 6.2. Exclusion Criteria

Candidates will be excluded if they meet any of the following criteria:

- a) Has undergone previous open knee surgery in the operative knee.
- b) Has a body mass index (BMI) > 40 kg/m^2.
- c) Is a candidate for bilateral TKA.\*  
*\*In the opinion of the Investigator, simultaneous bilateral TKA or staged bilateral TKA (where the second surgical procedure is to be scheduled within 6 months of the first procedure) is determined to be either: (i) clinically necessary or (ii) advised as the treatment plan to address acute symptoms and/or quality of life.*
- d) Has a coronal deformity greater than 20° or a sagittal flexion contracture greater than 15°.
- e) Has an active systemic infection or an active local infection in or near the operative knee joint, or has a previous history of joint infection.
- f) Has a pathological skeletal condition or skeletal immaturity which would significantly compromise the ability of the bone to withstand the stress required for preparation of the bones and proper implantation of the prostheses (e.g., severe osteoporosis, Paget's disease, renal osteodystrophy, AVN, sickle cell disease, etc.).
- g) Has femoral or tibial bone stock that is of poor quality or inadequate to provide stability for femoral or tibial fixation.
- h) Has any type of metallic implant in the operative leg.
- i) Has a known or suspected sensitivity to any of the materials in the investigational device or implant components (i.e. cobalt, chromium, titanium, stainless steel, titanium nitride, aluminum, polyethylene, PVC plastic)

#### THINK Surgical, Inc.

Proprietary rights of THINK Surgical, Inc. are involved in the subject matter of this material. It is submitted in confidence for a specific purpose and the recipient by accepting this material agrees that it will not be used other than for the express purpose for which it was delivered.

Disclosure to others without written permission from THINK Surgical, Inc. is forbidden.

- j) Has a systemic illness or a neuromuscular, neurosensory, or musculoskeletal deficiency that would render the patient unable to perform appropriate postoperative rehabilitation.
- k) Has a neuromuscular disorder that would create an unacceptable risk of prosthesis instability or fixation failure.
- l) Has significant comorbidities or conditions associated with high risk for surgical or anesthetic survival (e.g. peripheral vascular disease, unstable cardiac disease, poorly controlled diabetes, immunosuppression, etc.).
- m) Is pregnant or intends to become pregnant during the course of the study.
- n) Has previously experienced a stroke.
- o) Is participating concurrently in another clinical trial, or has participated in a clinical trial within the last 90 days, or intends to during the course of the study.
- p) Has a medical or psychiatric condition which, in the opinion of the investigator, poses a risk of the patient being unable to complete the study or presents risks associated with study participation.

### 6.3. Screening

The study population will be recruited from patients in the Investigators' practice who need unilateral total knee arthroplasty. Patients in this group will be screened for eligibility based on the inclusion and exclusion criteria described in Sections 6.1 and 6.2. All patient eligibility assessments will be initiated after completing the informed consent process. The screening process may include but will not be limited to a review of the patient's demographics, medical history, physical exam, standing long-leg AP x-rays, standard lateral x-rays, and current medications and therapies.

### 6.4. Informed Consent

Eligible patients will be recruited for the study by the Investigator and/or approved site staff. The Investigator or designee will provide eligible patients with a verbal overview of the study procedures and requirements, including all follow-up visit requirements. If the patient is willing to participate in the study, they will be asked to review the Informed Consent Form before they are officially enrolled in the study and asked to undergo any screening procedures or assessments. Each patient will be allowed sufficient time to decide whether they wish to participate in the study. If they agree to participate, they must sign and date the IRB-approved Informed Consent Form at or prior to the Baseline Visit. A copy of the signed Informed Consent Form will be given to the patient to take home for their records, and the original copy will be filed in the patient's study records.

#### THINK Surgical, Inc.

Proprietary rights of THINK Surgical, Inc. are involved in the subject matter of this material. It is submitted in confidence for a specific purpose and the recipient by accepting this material agrees that it will not be used other than for the express purpose for which it was delivered.

Disclosure to others without written permission from THINK Surgical, Inc. is forbidden.

Patients will be informed that they may decide to withdraw consent and discontinue their participation in the study for any reason at any time without facing any impact to their regular course of treatment at the study center.

## 6.5. Study Enrollment

Each Investigator shall maintain a Screening & Enrollment Log for all primary TKA patients that are recruited for the clinical trial and screened for eligibility. This log will be used to document all patients who agree to be screened, including the ones that withdraw consent during the screening process or are determined not to meet the eligibility criteria. If a patient is excluded from the study, the reason for exclusion will be recorded on the log. Patients who meet the eligibility criteria and consent to participate shall be assigned a unique Subject Identification Number that will be captured on the Screening & Enrollment Log and used to identify them on all source documents and Case Report Forms thereafter. Patients will be considered to be enrolled once they have signed the Informed Consent Form and been assigned a Subject Identification Number. Enrolled patients that elect to withdraw consent prior to treatment with the investigational device will be considered screen failures under inclusion criteria (e).

Patients who do not meet eligibility criteria will have the primary reason for ineligibility captured in the study database on the Eligibility Criteria eCRF. No other CRFs will be completed for these patients.

Once enrollment is complete in the IDE Study Arm, subjects will be enrolled into the Continued Access Arm.

## 7. STUDY PROCEDURES

Unless otherwise noted, the procedures below apply to both the IDE Study and the Continued Access arms of the study.

### 7.1. Baseline Visit (≤90 days prior to Date of Surgery)

A preoperative baseline clinical visit will be performed within 90 days prior to the patient's surgery, and will serve as a Standard of Care evaluation by the Investigator to confirm patient eligibility. Baseline Visit procedures may be completed in multiple clinic visits if required, but must be completed within 90 days prior to the date of surgery and the preoperative CT scan for surgical planning must be taken within 30 days prior to the date of surgery. Visit procedures will be recorded in the subject's study records and on the Baseline Visit eCRF.

